Overview: Each subject will attend a screening visit to determine eligibility for the study. If subjects are eligible, they will be scheduled to attend a baseline visit until which they will be asked to continue smoking in their normal manner in order to gather information on their baseline smoking patterns. At the baseline visit, subjects will be randomized to either the 'simulated menthol cigarette ban' or 'no menthol cigarette ban' conditions and additionally will be randomized to the order in which they will receive their assigned e-cigarettes (i.e., menthol flavored e-cigarettes followed by non-menthol tobacco flavored e-cigarette or vice versa). Based on their randomization, subjects will be instructed

as to whether they are to abstain from menthol cigarettes and will be provided a supply of e-cigarettes in the flavor they were randomized to for the first 4 week period. Subjects will be seen at visits scheduled approximately two and four weeks after starting use of their assigned e-cigarettes and will receive a phone call one week after starting use of their e-cigarettes to address any questions that arise. At the week four visit, subjects will receive a supply of the alternate e-cigarette products that they will use for the subsequent four week period. We do not believe that a washout period is needed based on a published cross-over study in which differences were found between menthol and tobacco flavored e-cigarettes after each was used for only a 7 to 10 day period (with no wash-out in between).²² During the second four week period, subjects will again receive a phone call 1 week after starting use of their assigned e-cigarette product and will be seen at visits scheduled two and four week after starting use of their assigned product. In order to ascertain if subjects change their tobacco use behavior once e-cigarettes are no longer provided by the study, subjects will have an additional follow-up visit 12 weeks after the baseline visit (i.e., four weeks after the end of the second assessment period). Subjects who complete the entire study will therefore be seen at a screening visit and 6 additional visits over an approximately 3 month period. The procedures occurring during each of these visits are described below.

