To the baseline visit, subjects will bring a first morning urine sample from which baseline urinary cotinine and total NNAL concentrations will be measured. Exhaled CO will be measured from a breath sample. Tobacco use behavior subsequent to the screening visit will be determined as will subjects' level of craving, withdrawal, motivation, self-efficacy to quit smoking, and support for a ban on a variety of menthol containing tobacco products. Subjects will then be told if they have been assigned to the condition in which they are to abstain from menthol cigarettes for the next eight weeks and will be provided (at no cost to them) with a two weeks supply of the product that they have been randomized to receive (i.e., menthol or tobacco flavored e-cigarettes, based on randomization) for the first four week period. Subjects will be instructed in how to properly use the product and will be given all of the packaging that normally accompanies the product. They will be told to use as much or as little of the product as they like. Subjects will also be provided with a tobacco use diary that they are to complete daily in which they are to record the number of cigarettes smoked and how often and how many puffs they used of their provided e-cigarette. Puffs per day has been used in other studies to evaluate e-cigarette use.^{22, 30, 31} They will additionally be asked to record use of any other tobacco or nicotine containing products. Subjects will also be asked to bring to all subsequent visits all e-cigarette cartridges as well as samples of the cigarettes or other tobacco or nicotine products that

they have been using in order to verify the accuracy of the smoking diary. Partially used cartridges will be weighed to determine the extent to which they were used. They will be given no specific instructions regarding using medicinal nicotine (i.e., nicotine patch, gum) or other tobacco products but will be asked to record any instances of using such products.

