Follow up visit: Subjects will attend one follow-up visit that will occur at week 12 of the study period (i.e., four weeks after they are no longer provided e-cigarettes). To this visit, subjects will again be asked to bring their first morning urine void and an exhaled CO will be measured. The final set of tobacco use diaries will be collected. Questionnaires assessing level of craving, withdrawal, motivation and self-efficacy to quit smoking, perceived health risk, and support for a ban on a variety of menthol tobacco products will be completed as in the evaluation visits. All subjects will be provided information regarding the smoking quitline as a resource available if they are interested in quitting smoking.

As the purpose of this formative proposed project is to provide pilot data for a subsequent grant submission, subjects will be asked at the end of the study ways in which to improve future studies addressing menthol e-cigarettes (for example, asking what they would change about the study and how honest they think others were in their reporting of menthol cigarette use). Subject responses will be examined for consistent themes so as to help inform study design for future projects.

Subjects will be paid \$20 for the screening visit, the baseline visit and each of the 5 subsequent visits (i.e., visits at week 2, 4, 6, 8, and 12). Subjects who complete all scheduled visits and have complied with study related procedures will receive a \$60 bonus. Subject can therefore receive up to \$200 for completing the study in addition to payment for points that were not redeemed for e-cigarette cartridges during the final two weeks of each evaluation period. Subjects will additionally be provided bus tokens (for those who take public transportation) or parking (for those who drive) for each visit.

Data and Safety Monitoring Plan:

In this study, one-half of smokers will be asked to stop using menthol cigarettes and all smokers will be provided e-cigarettes to use over a 2 month period. Those randomized to abstain from smoking menthol cigarettes will be given no specific instructions regarding modifying their smoking

behavior in order to more closely mimic what would occur if menthol cigarettes were banned. Based on our previous research, it is expected that most will smoke non-menthol cigarettes instead.

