To ensure confidentiality, all subjects enrolled in the study will be assigned a study identification code which will be used on all study related data collection forms except for those on which the use of personal identifiers is mandatory (e.g., informed consent form). Forms that link the name of the participant and the subject identification code will be kept in a locked cabinet or office or in an electronic file stored on password protected secure computer servers that meet university guidelines. Access to subject identifiable information will be limited to those that require this information such as investigators or others who have direct contact with study subjects (e.g., study coordinator).

At each visit, subjects will be asked if they are experiencing any adverse effects or difficulties with the study. The Principal Investigator will review reports with study staff to determine if changes are needed to any of the study related procedures or if the subject has symptoms/difficulties that would warrant discontinuation from the study.

Data Analysis

The primary aim of the proposed study is to compare changes in each outcome measure (e.g., number of cigarettes smoked, amount of e-cigarette used, motivation to quit smoking, biomarker concentrations, support for a menthol ban) between the four week period when subjects are provided menthol e-cigarettes compared with the four week period when subjects are provided tobacco flavored e-cigarettes. An additional aim is to determine if cigarette type (i.e., randomization to menthol vs non-menthol) moderates the effects of e-cigarette type.

Outcomes will be described using means and standard deviations, separately for each combination of visit and experimental condition (menthol cigarettes available or not, menthol or non-menthol tobacco flavored e-cigarette). Skewed variables will be log transformed and their geometric means and 95% confidence intervals will be reported. Hypothesis testing will be performed using linear mixed models, with fixed effects for randomization group and time, and a random subject effect. The study is designed to provide pilot data to estimate broad trends and parameters that can be used

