to plan larger studies. Enrolling a total of 40 subjects with 15-20% attrition would leave at least 16 subjects per group to compare menthol vs. no menthol cigarettes allowed, and those 16 can be compared within each group to test the effects of e-cigarette flavor since all subjects will receive both flavor options in a crossover design. This would result in approximately 80% power to conclude significance at the two sided 0.05 level if the true effect size is 1.0.

The results of this study will be used to plan future projects that would more definitively address the question of how menthol flavoring in e-cigarettes should be regulated. This formative study would inform future research by 1) demonstrating the acceptability of menthol and non-menthol flavored e-cigarette use in this population; 2) providing pilot data regarding how menthol flavoring in e-cigarettes affects (in the presence and absence of a simulated ban on menthol cigarettes) smoking changes, thereby enabling more informed hypotheses to be developed and more accurate sample size calculations to be performed and 3) providing information for study design refinement via the descriptive data collected from participants regarding their recommendations for future study designs.

Data and Record Keeping:

Data will be managed by the study coordinator(s). To ensure confidentiality, all subjects will be assigned a study identification code to be used on all data collection forms except those for which use of personal identifiers is mandatory (e.g., informed consent form). Forms that link the name of the participant and the subject identification code will be kept in a locked cabinet or office or in an electronic file stored on password protected secure computer servers. Access to subject identifiable information will be limited to those that require this information such as study investigators or others who have direct contact with study subjects (e.g., study coordinator).

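### The mixed model leaves out the baseline values the trial collects, so the ban versus no-ban comparison is less precise than it could be; the flavor and moderation aims are largely unaffected

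*Combined protocol and SAP*

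**What the plan says.** The Data Analysis section gives the whole hypothesis-testing model in one phrase: "linear mixed models, with fixed effects for randomization group and time, and a random subject effect". It names no baseline covariate and no group-by-time term, and it does not say which visits supply responses.

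Baseline data are nevertheless collected deliberately. The Implementation Plan overview asks subjects to keep smoking as usual until the baseline visit "in order to gather information on their baseline smoking patterns". At that visit "baseline urinary cotinine and total NNAL concentrations will be measured", along with exhaled CO, craving, withdrawal, motivation, self-efficacy and support for a ban. Only then are subjects told their ban assignment.

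The power statement, also in Data Analysis, says: "Enrolling a total of 40 subjects with 15-20% attrition would leave at least 16 subjects per group". The stated use of those groups is "to compare menthol vs. no menthol cigarettes allowed", and the claim is "approximately 80% power to conclude significance at the two sided 0.05 level if the true effect size is 1.0".

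**The concern.** A pre-randomization value of the same outcome usually predicts the later value. Using it as a covariate removes part of the between-subject variance from a between-group comparison. With about 16 subjects per arm, that variance dominates the error of the ban versus no-ban contrast. The trial pays for the baseline measurements and then does not say how they enter the analysis.

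What is at stake is the width of the interval around the ban effect. This is a pilot whose estimates are meant to feed the sample size of a larger study, so an avoidably large residual variance would carry into that planning.

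A second, conditional issue comes from the same phrase. The ban runs for eight weeks, so baseline and week 12 are off-ban. If those visits were entered as responses under a single group effect held constant over time, the estimated ban effect would average on-ban with off-ban visits.

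**Working it through.** **Inputs from the documents.** 40 enrolled, up to 20% attrition, half allocated to the ban: 40 × 0.80 / 2 = 16 per group. Two-sided alpha 0.05, effect size 1.0. Visits: baseline, weeks 2, 4, 6, 8, and follow-up at week 12. Urine: baseline, weeks 4, 8 and 12.

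**Assumptions.** The documents give no correlation between baseline and later values, so I use ρ = 0.3, 0.5 and 0.7. I take the same value between any two visits of one subject, and read effect size 1.0 in units of the SD at a single visit.

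**Step 1: the plan's own figure.** Two-sample t-test, noncentrality 1.0 / √(2/16) = 2.83, 30 df: power 78%. The normal approximation gives 81%. Both match the stated 80%. A paired test of flavor in 16 subjects at the same effect size would give 96%, so the stated figure belongs to the unadjusted two-group comparison.

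**Step 2: baseline covariate, one visit.** Residual variance is 1 − ρ². Power uses noncentrality 2.83 / √(1 − ρ²), with 29 df and the SD inflated by √(1 + 1/28) for estimating the slope.

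| ρ | variance removed | power without baseline | power with baseline |
|---|---|---|---|
| 0.3 | 9% | 78% | 80% |
| 0.5 | 25% | 78% | 87% |
| 0.7 | 49% | 78% | 96% |

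**Step 3: the four on-ban visits averaged.** This is closer to what a repeated-measures model does. The variance of the mean is V = ρ + (1 − ρ)/4; with the covariate it is V − ρ².

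| ρ | V | V − ρ² | power without baseline | power with baseline |
|---|---|---|---|---|
| 0.3 | 0.475 | 0.385 | 98% | 99% |
| 0.5 | 0.625 | 0.375 | 93% | 99% |
| 0.7 | 0.775 | 0.285 | 87% | over 99% |

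Power is near its ceiling at effect size 1.0, so interval width is more informative. The ratio √((V − ρ²)/V) is 0.90, 0.77 and 0.61: intervals about 10%, 23% or 39% narrower, before a small-sample penalty of about 2%.

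**Step 4: urine markers.** Only weeks 4 and 8 are on-ban, so V = ρ + (1 − ρ)/2 = 0.65, 0.75, 0.85. By the same formulas, power is 92%, 88% or 84% without baseline and 95%, 97% or 99% with it.

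**Step 5: the conditional dilution.** In balanced data with a random intercept and one constant group effect, the estimate is the average over all rows. If every visit is a row and no effect remains at week 12, the ban effect is multiplied by 4/6 for CO and most questionnaires, and by 2/4 for urine markers. For the six-visit case at ρ = 0.5, V = 0.5 + 0.5/6 = 0.583 and power is 67%, against 93% from the four on-ban visits. If the effect persisted fully at week 12, the factor would be 5/6 and power 85%.

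**The case against.** The strongest case against the point is one of scope. Neither numbered aim tests the ban main effect. Aim 1 compares flavors within subject, and Aim 2 asks whether the ban changes that within-subject difference. A single baseline value largely cancels from both. Randomization also keeps an unadjusted comparison of on-ban visits unbiased, and a pilot may reasonably use a simple model. All of this stands, and it confines the point to precision of one contrast. It does not remove the point, because the power paragraph sizes the groups for exactly that contrast.

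It might also be said that the plan already uses baseline, since the primary aim is worded in terms of changes. That word is attached to the comparison of the two flavor periods and is not defined as change from baseline. Even if it were, change scores do no better than a covariate: by the normal approximation at a single visit, power is 67%, 81% and 96% at ρ = 0.3, 0.5 and 0.7, against 84%, 90% and 98%.

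Three stronger readings are tempting, and the documents do not support them:

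- *The ban effect will be diluted.* The text neither states nor excludes entering off-ban visits under a constant group effect. Its focus on the two four-week periods points toward weeks 2 to 8. The 4/6 and 2/4 factors also need the effect to have vanished by week 12, which is the question the follow-up visit is there to answer.
- *The ban comparison is underpowered without baseline.* Under these assumptions, averaging the on-ban visits already exceeds the planned 80%.
- *Baseline is the largest available source of precision.* At ρ = 0.5, averaging four visits removes 37.5% of the single-visit variance (1 − 0.625), more than the 25% from baseline. The order reverses at 0.6 (30% against 36%).

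**Conclusion.** The point holds as a matter of precision, for the ban versus no-ban comparison only. At a single visit the gain at effect size 1.0 runs from about 2 percentage points of power (ρ = 0.3) to about 18 (ρ = 0.7). With the four on-ban visits averaged it runs from about 1 to about 12 points. These sizes rest on an assumed correlation, assumed equal across visits, and on effect size 1.0 being in single-visit SD units; at low correlation the benefit is small.

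The dilution is a gap in specification: the plan should say which visits enter the model. It is not a demonstrated bias.

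**What to change.** Add to Data Analysis, for the ban comparison:

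- Responses are the on-ban values: weeks 2 to 8, or weeks 4 and 8 for urine markers.
- The subject's baseline value of the same outcome is a covariate, on the log scale where the outcome is logged. A constrained baseline with group-by-time terms is an equivalent choice.
- Week-12 persistence is estimated as its own contrast, also adjusted for baseline, and is not pooled with the on-ban visits.

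Outcomes with no baseline measurement are exempt: e-cigarette use, product liking and perceived health risk of the product.

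The cost is one sentence of analysis text and one degree of freedom, with no new visits, samples or questionnaires.
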